6. Subject is willing and able to refrain from engaging in any non-study procedure therapies for the management of his or her neck/shoulder pain throughout the course of study participation, including conventional therapies such as physical therapy, occupational therapy and hot or cold packs, as well as alternative therapies such as chiropractic care and acupuncture
7. 18 years of age or older
8. Male or female
9. Primary language is English

EXCLUSION CRITERIA

A subject who satisfies any of the following criteria will be excluded from study participation:

1. Presenting primary pain is located outside or in addition to the region of the neck (right side/left side/back) or the shoulder (right and/or left side)
2. Etiology of neck/shoulder pain cannot be definitively diagnosed; or has been diagnosed as being in whole or in part other than that of osteoarthritis, chronic muscle spasms or cervical and thoracic spine sprain strain; or other potentially contributing etiologies cannot be satisfactorily ruled out
3. Pain is acute: symptoms prevailed for fewer than each of the prior 30 days
4. Current active chronic pain disease: such as chronic fatigue syndrome and fibromyalgia
5. Use of analgesics or muscle relaxants within 7 days prior to study procedure administration
6. Use of systemic corticosteroid therapy (inhaled and topical corticosteroids permitted), narcotics or Botulinum toxin (Botox®) injection in the neck / shoulder region within 30 days prior to study procedure administration
7. Active cancer or treatment for cancer within the last 6 months
8. Unstable cardiac disease, such as recent cardiac arrhythmia, congestive heart failure or myocardial infarction
9. Prior surgery to the neck/shoulder region
10. Known herniated disc injury
11. Active infection, wound or other external trauma to the areas to be treated with the laser
12. Medical, physical, or other contraindications for or sensitivity to light therapy
13. Serious known mental health illness such as dementia or schizophrenia; psychiatric hospitalization in the past two years
14. Pregnant or breast feeding
15. Participation in a research study within the past 30 days

PRE-PROCEDURE EVALUATIONS

The pre-procedure evaluation phase directly follows successful study qualification, on the same day.

BASELINE VARIABLES

- Neck / Shoulder Pain Variables
- Concomitant Medication and Therapy Use
- Subject Demographics

OUTCOME ASSESSMENTS

- Visual Analog Scale (VAS) Degree of Pain Rating
- Linear Range of Motion (ROM)

PROCEDURE ADMINISTRATION PHASE

PROCEDURE ADMINISTRATION PROTOCOL

- The procedure administration phase of the study directly follows successful completion of the pre-procedure evaluations phase, on the same day.
- The procedure administration phase comprises a single procedure administration with the Erchonia® GVL.
- The procedure administration lasts a total of 13 minutes.
- The procedure administration with the Erchonia® GVL is administered at the test site.
- The procedure administration protocol is identical to that in the retrospective control study, and is as follows:
 1. The subject enters the procedure room and is seated comfortably.
 2. The subject is correctly fitted with the protective eyewear.
 3. The Erchonia® GVL is positioned and centered 6 inches above the subject's sagittal suture (top of the head).
 4. One minute of pulsed laser is applied to the sagittal suture (top of the head).
 5. Two minutes of pulsed laser is then applied to the left cervical, shoulder and torso area. The laser is applied starting in the cerebral region, at the top of the ear, lasering left cervical anterior and posterior muscles, working the laser down into the left shoulder and torso anterior and posterior muscles.
 6. Step 5 is repeated to the subject's right cervical shoulder and torso area.
 7. One minute of pulsed laser is then applied to right shoulder during passive external rotation of the shoulder. The anterior muscles of the right shoulder (pectoralis group) are lasered, with the subject's arm bent at the elbow.
 8. One minute of pulsed laser is then applied to the right shoulder during passive adduction of the subject's right arm and shoulder. The posterior muscles of the right shoulder are lasered.
 9. One minute of pulsed laser is then applied to the right cervical muscle and trapezius muscle during passive left lateral flexion of the cervical spine. Starting in the neutral position of the head, the laser light is applied to the right cervical muscles and right trapezius muscles.
 10. One minute of pulsed laser is then applied to the right sternocleidomastoid and scalene muscles during passive range of motion. The laser light is applied to the right sternocleidomastoid and scalenus muscles.
 11. Step 7 is then repeated to the left shoulder.
 12. Step 8 is then repeated to the left shoulder.
 13. Step 9 is then repeated to the left cervical spine.
 14. Step 10 is then repeated to the left sternocleidomastoid and scalenus muscles.
 15. The subject's protective eyewear is removed, and the single procedure administration session is over.

Justification for the Procedure Administration Protocol

The procedure administration protocol in this current study is identical to that which was evaluated in the comparative retrospective EVRL study to enable direct comparison of findings between the two studies and statistical analysis of different group outcomes.

PROCEDURE ADMINISTRATION PHASE EVALUATIONS: STUDY ENDPOINT

Within 3 minutes of completion of the procedure administration phase, study endpoint evaluation will occur.

OUTCOME ASSESSMENTS

- Visual Analog Scale (VAS) Degree of Pain Rating
- Linear Range of Motion (ROM)
- Subject Satisfaction with Study Outcome Rating
- Adverse Events Evaluation

POST-PROCEDURE ACTIVITIES

The post-procedure evaluation phase of this study will commence immediately following completion of the procedure administration phase evaluations and will last for 2 days (48 hours).

The post-procedure outcome assessments will be recorded by the subject in his or her own home on forms provided by the test site. The subject will be instructed on when and how to complete the forms and how to return them to the test site prior to leaving the test site on the procedure administration day.

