ERCHONIA® GVL

**An Evaluation of the Effect
of the Erchonia® GVL Green and Violet laser
on Neck and Shoulder Pain**

ERCHONIA CORPORATION

**Version 1.0
July 31, 2020**

NCT04895618

TABLE OF CONTENTS

STUDY INFORMATION.....	1
SPONSOR.....	1
REGULATORY CONSULTANT	1
CLINICAL CONSULTANT	1
MONITOR.....	1
PRINCIPAL CLINICAL INVESTIGATORS & TEST SITES.....	1
INSTITUTIONAL REVIEW BOARD.....	2
PURPOSE OF STUDY	2
STUDY DURATION	2
INDICATION FOR USE	2
EXPECTED RESULTS	2
DEVICE INFORMATION: ERCHONIA® GVL	3
STUDY INDICATION, THEORY OF MECHANISM OF OPERATION & SUPPORTING MATERIALS	9
STUDY DESIGN	24
SUBJECT GROUP	24
BLINDING	24
RADNDOMIZATION.....	24
SUBJECTS	24
STUDY TEST BATTERY	27
STUDY PROCEDURE PROTOCOL.....	30
PRE-PROCEDURE ACTIVITIES.....	30
STUDY QUALIFICATION	30
PRE-PROCEDURE EVALUATIONS	32
PROCEDURE ADMINISTRATION PHASE	33
PROCEDURE ADMINISTRATION PHASE EVALUATIONS: STUDY ENDPOINT ..	34
POST-PROCEDURE ACTIVITIES.....	34
24 HOUR AND 48 HOUR POST-PROCEDURE EVALUATIONS.....	34
ADVERSE EVENTS	35
PRIVACY AND CONFIDENTIALITY	35
STATISTICAL ANALYSIS.....	36
INFORMED CONSENT	38

STUDY INFORMATION

SPONSOR

Erchonia Corporation
[name]
[name]
Contact: [name], President
[contact]
E-mail: [contact]

CLINICAL & REGULATORY CONSULTANT

Regulatory Insight, Inc.
Nashville Office
[name]
[name]
Contact: [name], Clinical Consultant
[contact]
E-mail: [contact]

MONITOR

Erchonia Corporation
[name]
[name]
Contact: [name]
[contact]
E-mail: [contact]

PRINCIPAL CLINICAL INVESTIGATORS AND TEST SITES

- [name], DC, DACBN,
New York ChiroCare
[name]
[name]
[contact]
E-mail: [contact]
- [name], DC, DACNB
[name] Chiropractic Clinic
[name]
[name]
[contact]
E-mail: [contact]
- [name] DC,
[name] Laser Chiropractic
[name]
[name]
[contact]
Email: [contact]

INSTITUTIONAL REVIEW BOARD

Western Institutional Review Board® (WIRB®)
[name]
[name]
[contact]
WIRB Tracking #: 20202480

PURPOSE OF STUDY

The purpose of this clinical study is to determine the effectiveness of the Erchonia® GVL (manufactured by Erchonia Corporation (the Company), when both the green and violet diodes are activated simultaneously, in providing temporary relief of minor chronic neck and shoulder pain of musculoskeletal origin.

INDICATION FOR USE

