There will be a single subject group in this study. All subjects will receive the active study procedure with the green and violet diodes of the Erchonia® GVL emitted simultaneously.

Comparative subject data for Erchonia® EVRL emitting the red and violet diodes simultaneously will be taken from the 2019 study whose results supported FDA market clearance for K191257.

BLINDING

As all subjects in this study will receive the active procedure administration with the Erchonia® GVL, neither subjects nor investigators will be blinded. The statistician analyzing the study results will however be blinded with respect to study success analysis. The data from this current GVL study and the retrospective data from the 2019 EVRL study will be deidentified and presented to the study statistician as 'Group A' and 'Group B'. The statistician will not be aware of which group – A or B – contains the current GVL study data and which contains the retrospective comparative EVRL study data.

RANDOMIZATION

As this study is a single treatment group study, randomization to procedure group is not applicable. Therefore, this is a non-randomized trial.

SUBJECTS

Subject Sample

Subjects will be males and females 18 years or older who present with chronic (30 consecutive days or longer) neck and/or shoulder pain diagnosed as being of musculoskeletal origin (osteoarthritis, chronic muscle spasm, cervical and thoracic spine sprain strain).

Sample Size

There will be 43 qualified subjects enrolled in this study.

Rationale for Sample Size

Sample size is determined to be identical to that intended to be enrolled in the comparative reference EVRL study.

Recruitment

Subjects may be recruited from among:

- (i) The Principal Investigator's/test site's pool of existing and new patients
- (ii) Referrals from other suitable medical clinics and professionals
- (iii) Subjects who respond to the following recruitment materials:

a) Flyer

WANTED

**ADULTS WITH NECK AND SHOULDER PAIN
ONGOING FOR THE LAST 30 DAYS FOR A
CLINICAL STUDY OF THE EFFECTS OF
LOW LEVEL LASER LIGHT ON
REDUCING NECK AND SHOULDER PAIN**

**THIS STUDY INVOLVES A SINGLE
LASER LIGHT PROCEDURE
WITH THE ERCHONIA® GVL LASER
AT THE TEST SITE**

FOR MORE INFORMATION PLEASE CONTACT:

<PI name>
<test site name & location>
<phone # and/or e-mail>

b) Newspaper Ad

Neck and Shoulder Pain Research Study

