- (i) Over the counter and prescription medications currently used to relieve neck/shoulder pain, including duration, dosage, and frequency of use
- (ii) Non-drug treatments/therapies (conventional, alternative, and experimental) currently used to relieve neck/shoulder pain, including duration and frequency or use/application
- (iii) Over the counter and prescription medications currently used, and therapies currently engaged in for any non-pain relief indication, including duration, dosage, and frequency of use

SUBJECT DEMOGRAPHICS: Age, gender, and ethnicity

OUTCOME ASSESSMENT TOOLS

VISUAL ANALOG SCALE (VAS) DEGREE OF PAIN RATING

Subjects will be asked to rate the overall degree of pain experienced in the neck / shoulder region on the following 0-100 mm (0 -10 cm) Visual Analog Pain Scale, by responding to the following question:

"Using the scale below, please mark with a cross (X) a SINGLE SPOT along the 0 to 100 line below that best shows how much pain you feel in your neck / shoulder right now. '0' means you feel no pain at all and '100' means you feel the worst pain imaginable. PLEASE MARK ONLY ONE SPOT. DO NOT THINK OF OR WRITE IN A NUMBER."

The Visual Analog Pain Scale (VAS) is one of the three most commonly used scales for assessing chronic pain. It is a simple scale that consists of a line anchored at one end by a label such as "NO PAIN" and at the other end "WORST POSSIBLE PAIN". The subject marks on the line the spot for the pain intensity, which is then measured.

Standard guidelines for effective use of the VAS that are followed in this clinical study are:

- i. The line should be 10, 15 or 20cm long, as other lengths are less reliable.
- ii. There should be a small vertical mark at each end, with numbers 0 and 100, and a verbal description.
- iii. The verbal description must be in absolute terms (e.g., worst pain imaginable);
- iv. The line itself should be clear of any markings and should be horizontal rather than vertical, for more reliable measurements.

Used in the above way, it has been shown that the VAS is a proper ratio scale. Like a thermometer, this means that its two ends are rooted, and a doubling of the score does accurately reflect a doubling of the pain. Consequently, sensitive t-tests and ANOVA methods can be used in the analysis, so that significant differences can be identified with relatively small sample sizes or small differences between groups.

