Subjects' identities will be kept confidential by assigning each subject a subject ID upon acceptance into the study. The subject ID will comprise the investigator's two initials (first and last name initials) and a three-digit number that will be based upon the subject's order of entry into the clinical study. Each test site will be assigned a unique range of numbers. Test site #1 will be assigned numbers 001 to 100 (Subject ID RS001 to RS100). Test site #2 will be assigned numbers 101 to 200 (Subject ID AC101 to AC200). Test site #3 will be assigned numbers 201 to 300 (Subject ID KG101 to KG200). For example, the eighth subject to be enrolled at test site #2 would have a subject ID of AC108. Neither the study Sponsor nor Regulatory Insight, Inc. will receive any additional identifying information about a subject and will therefore have no way of linking a Subject ID to a particular subject and his or her results.

STATISTICAL ANALYSIS PLAN

PRIMARY EFFICACY OUTCOME MEASURE: CHANGE IN SUBJECT SELF-REPORTED VAS PAIN RATING FROM BASELINE TO STUDY ENDPOINT

The primary efficacy outcome measure for this clinical study is the change in subject self-reported Visual Analog Scale (VAS) pain rating from baseline to study endpoint evaluation, with study endpoint defined as within 3 minutes of completion of the study single procedure administration with the Erchonia® GVL laser.

Individual Subject Success Criteria

Individual subject success criteria is defined as a 30% or greater decrease in self-reported VAS pain rating at study endpoint relative to baseline.

Overall Study Success Criteria.

Overall study success criteria is defined as at least $75\% \pm 5\%$ of subjects (70% to 80%) meeting the study individual success criteria.

Justification for Study Success Criteria

The clinical relevance and statistical justification of the individual subject and overall study success criteria is as follows:

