- A t-test for two independent sample will be performed to evaluate the significance of the difference in the mean change in VAS pain scores from baseline to endpoint evaluation between the two study groups (GVL vs EVRL) to evaluate for equivalency to support the support the conclusion of the proportion of successes evaluation. Significance levels will be considered at the p<0.05 level.

SECONDARY EVALUATIONS

The following secondary evaluations will be performed on the GVL study data set. As no claims are intended to be made based on the secondary measures, the findings are presented through descriptive analysis and qualitative trending only, without evaluation for or claims of statistical significance.

- Change in mean VAS ratings across study duration: all study evaluation points (baseline, endpoint, 24 hours and 48 hours post-procedure).
- Change in linear ROM measurements across respective study evaluation points at study baseline and endpoint.
- Subject satisfaction with study outcome ratings across study duration.

INDIVIDUAL TEST SITES

Results will be presented by individual test site for comparison.

INDIVIDUAL SUBJECT RESULTS

Individual subject results for study outcome measures will also be presented.

SAFETY ANALYSES

Safety analyses will be based on all enrolled subjects and will be assessed by evaluating and comparing frequency and incidence of observed and/or reported adverse events between subjects in the GVL and the EVRL studies. A chi-square test with a continuity correction will be performed to compare the percentage of subjects who had adverse events between the two subject groups.

INFORMED CONSENT

- Informed consent will be an agreement between the individual investigator and each subject, having the capacity to understand and make an informed decision. Consent will be obtained prior to each potential subject's participation in this clinical study.
- Each subject participating in this clinical study will be made aware of the fact that his or her participation involves research and the intent of the research, the expected duration of his or her participation and a description of the procedures that will be followed.
- Each subject will be made aware of the reasonably expected benefits he or she might receive, as well as any risks or potential discomfort that are involved.
- Each subject will also be made aware of alternative treatments available to him or her.

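### Sites may enrol their own patients, but past low-level laser treatment and earlier EVRL enrolment are neither excluded nor listed for recording, so selection of earlier responders could go unseen

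*Combined protocol and SAP*

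**What the plan says.** **Who may be enrolled.** The Recruitment section gives three sources: the sites' own patients ("The Principal Investigator's/test site's pool of existing and new patients"), referrals, and people who answer the flyer or newspaper advertisement. Both advertisements say that the study is of laser light. One of the three listed sites has "Laser Chiropractic" in its practice name.

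**What is excluded.** None of the 9 inclusion or 15 exclusion criteria mentions past low-level laser treatment, past response to it, or the EVRL study. The nearest are:
- exclusion 12, on contraindication or sensitivity to light therapy;
- exclusion 15, "Participation in a research study within the past 30 days";
- inclusion 6, on refraining from other therapies during the study.

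**What is recorded.** The Study Test Battery lists "Non-drug treatments/therapies (conventional, alternative, and experimental) currently used to relieve neck/shoulder pain, including duration and frequency or use/application". Patient history is one of the diagnostic tools, but its stated content for each diagnosis (trauma, injury, restricted motion, relief from heat or massage) does not include laser treatment.

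**How success is judged.** "There will be 43 qualified subjects enrolled in this study", in one unblinded group. "Individual subject success criteria is defined as a 30% or greater decrease in self-reported VAS pain rating at study endpoint relative to baseline", and the endpoint is within 3 minutes of the procedure. The SAP declares non-inferiority if the observed proportion is not below 70%, which is the EVRL rate of 75% less a 5-point margin. Two comparisons with the EVRL data support this. One is a test of proportions. The other is described as follows: "A t-test for two independent sample will be performed".

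**The concern.** The sponsor's red and red/violet lasers are already cleared for this indication, so some eligible patients may have been treated with one. A patient whom laser treatment helped may be more likely than others to respond again, or to report a response in an open study. There is no concurrent randomised arm to share that selection, so it would go straight into the primary proportion.

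Because past exposure is not a listed variable, no planned analysis could separate laser-naive from laser-experienced subjects. The by-site and individual-subject presentations might show an outlying site but could not explain it.

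The second issue is overlap. A 2019 EVRL subject who enrolled again would contribute to both groups of a test that assumes independence. The statistician receives de-identified Groups A and B, and the sponsor holds only subject IDs, so neither could detect this.

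**Working it through.** **1. The plan's own figures.** The sample size has no calculation to reproduce: "Sample size is determined to be identical to that intended to be enrolled in the comparative reference EVRL study". The cut-off reproduces as 75% − 5% = 70%. With n = 43, 0.70 × 43 = 30.1. So 30/43 = 69.8% fails and 31/43 = 72.1% passes, and the rule is at least 31 successes.

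**2. Does exclusion 15 reach EVRL subjects?** The reference study is dated 2019 and this protocol July 31, 2020. From the last day of 2019 to the protocol date is 31 + 29 + 31 + 30 + 31 + 30 + 31 = 213 days, well beyond 30. The exclusion would not stop an EVRL participant.

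**3. Effect on the chance of passing.** The documents give neither the share of laser-experienced patients nor their success rate, so every rate here is an assumption. Let p be the true success rate in laser-naive subjects, and let k laser-experienced subjects have rate q. Then

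P(pass) = P(X + Y ≥ 31), with X ~ Bin(k, q) and Y ~ Bin(43 − k, p).

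For the mixed row, X is the sum of Bin(5, 0.90) and Bin(4, 0.40).

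| Laser-experienced subjects (of 43) | p = 60% | p = 65% |
|---|---|---|
| None | 7.0% | 20.9% |
| 9: five at 90%, four at 40% | 9.6% | 22.5% |
| 4 at 90% | 13.0% | 31.0% |
| 9 at 75% | 14.2% | 30.0% |
| 9 at 80% | 17.5% | 35.2% |
| 9 at 85% | 21.3% | 40.8% |
| 9 at 90% | 25.5% | 46.7% |

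The mixed row has an average rate of (5 × 0.90 + 4 × 0.40)/9 = 67.8%, close to the naive rates, and so moves little. The lift depends on the laser-experienced subjects doing better on average than the others.

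**4. How many would bring the expected rate to 70%?** Solve k·q + (43 − k)·p = 0.70 × 43, which gives k = 43(0.70 − p)/(q − p), rounded up. With q = 90%:
- p = 65%: 43 × 0.05/0.25 = 8.6, so 9 subjects;
- p = 60%: 43 × 0.10/0.30 = 14.3, so 15 subjects.

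Over p from 55% to 65% and q from 85% to 95%, the answer runs from 8 to 22 subjects, or about 19% to 51% of the sample.

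**The case against.** **The mechanism is inferred.** No section says that any site has treated neck or shoulder pain with a laser, holds known responders, or took part in the EVRL study. Clearances show that devices may be marketed, not that these patients received them. A reader might infer from one practice name that the sites will fill the study with proven responders. The documents do not support that: the name gives neither device, indication nor patient numbers, and it belongs to one site of three. This objection stands, and it limits the point to a gap in the plan.

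**The reference may carry the same selection.** The 70% floor comes from the EVRL result. If EVRL also took laser-experienced patients, its 75% already contains the effect and the comparison is closer to like with like. This stands as an unknown, because EVRL recruitment and eligibility rules are not given. It cannot be settled without the missing variable.

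**The size is assumed.** Past non-responders are as eligible as responders, and a response to red or red/violet light need not carry over to green/violet. With 13 of 43 subjects all at 90%, the chance of passing would be 39.7% or 60.6% (p = 60% or 65%). A reader might take such figures as the expected effect, but they need every laser-experienced subject to be a strong responder, and nothing in the documents shows that.

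**Some information is captured.** Current laser treatment falls under non-drug therapies, including experimental ones. It would be wrong to say that nothing identifies laser users. The case report forms are in an appendix whose content is not available, so the point rests on the listed variables. Past use and response are still absent from that list.

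**Overlap touches only the supporting tests.** Correct: the loss of independence does not alter the 31-of-43 rule itself.

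**Conclusion.** The gap is in the text: existing patients may be enrolled, past laser treatment and EVRL participation are not addressed by any criterion, and past exposure and response are not listed for recording. Whether this would bias the result is not established.

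For 4 to 9 laser-experienced subjects with the assumed mixes and rates above, the chance of a device with a true laser-naive rate of 60% passing moves from 7.0% to between 9.6% and 25.5%. For a rate of 65% it moves from 20.9% to between 22.5% and 46.7%. The low end is nearly no change, and there would be no lift if laser-experienced subjects did no better on average than the rest.

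The documents do not support the stronger reading that GVL would pass because of who was enrolled. They support the narrower one: if such selection occurs, the plan has no means of seeing it. This should be changed because the remedy is cheap and the result is meant to support a 510(k) submission.

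**What to change.** 1. Add an exclusion for earlier participation in the EVRL neck and shoulder study. Sites can check this when they take the history, and it protects the independence of the two groups.
2. Add one baseline item: any earlier low-level laser treatment of the neck or shoulder (yes/no, last date, whether it helped).
3. Pre-specify the success proportion in laser-naive subjects as a sensitivity analysis beside the ITT result, and state that the EVRL reference may not be laser-naive.

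Do not exclude all laser-experienced patients unless the EVRL study did the same. If EVRL admitted them, a blanket exclusion would create a mismatch with the only comparator. The same caution applies when reading the laser-naive figure against the EVRL-derived 70%.

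The cost is one criterion, one form item and one row in the results table, with a slightly smaller recruitment pool and a less precise estimate in the subset.
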